### **9.5.2. Study Materials for SMC Review**

The primary focus of the SMC will be to independently review all SAEs and items that PATH refers to it. The SMC will accomplish this by evaluating all such events against the known or expected safety profile of the study vaccine. Clinical and laboratory data, clinical records, and other study-related records will be made available for the SMC, as appropriate and available. If necessary, special reports will be prepared by the investigator or PATH.

It is the responsibility of the investigator and PATH to ensure that the SMC is apprised of all new safety information relevant to the study vaccines and the study. Summary safety and enrollment data will be forwarded periodically to the SMC. The SMC will receive all protocol revisions and might receive other documents related to the study.

### **9.5.3. Reports from the SMC**

#### **9.5.3.1. Review Report**

According to pre-specified criteria agreed upon by PATH, the SMC will communicate in writing its findings and any concerns and recommendations to PATH. Unless otherwise specified, the written report will then be forwarded to the investigator, who may, in turn, submit the report as per local independent ethics committee (IEC) policy.

#### **9.5.3.2. Immediate Action Report**

The SMC will notify PATH of any findings of a serious and immediate nature including any recommendations to discontinue all or part of the trial. In addition to any verbal communications, recommendations to discontinue or substantially modify the design or conduct of a study must be conveyed in writing on the day of the SMC review. This written, confidential report may contain unmasked supporting data and include the SMC's rationale for the recommendations.

### **9.6. Halting Rules**

Given the experience with CD-JEV and MMR vaccine, no safety issues are anticipated which would result in the suspension of enrollment in the study. However, the trial might be suspended at any time by PATH or any ethical review committee overseeing this study for any safety concern. This includes, for example, and without limitation, an SAE resulting in death, an unexpectedly high number of persons experiencing a similar event after receipt of any dose, or an unusually high rate of SAEs. PATH may suspend the study in the event that study conduct is found to be below GCP standards.

Should an SAE occur which is likely related to administration of study vaccine, the decision whether the study should continue per protocol, proceed with caution, be suspended pending further investigation, be discontinued, or be modified and then proceed will be made by PATH in consultation with the investigator, the SMC, the RITM institutional review board (IRB), and/or Western IRB (WIRB). However, no rules will be pre-specified to define these conditions.

If the study is halted, participants will be contacted immediately explaining why the study has been halted and the implications for their medical well-being.

In the event of the appearance of new data that indicate an increased level of risk to study participants, the clinical trial will be suspended until PATH, the SMC, and all ethical review committees have reviewed relevant data and agreed that the trial may proceed.

## **10. CLINICAL MONITORING**

### **10.1. Site Monitoring Plan**

Qualified and appropriately trained individuals will carefully monitor the study. The study monitor will periodically contact the site and perform on-site visits. The extent, nature, and frequency of site visits will be based on such considerations as study objectives, study design and complexity, and enrollment rate; periodicity and nature of monitoring activities will be described in the Monitoring Plan. PATH may

also include representatives of the Bill & Melinda Gates Foundation (the Foundation) in site contacts and visits, as appropriate, and will keep the Foundation program officer apprised of study progress.

#### **10.1.1. Site Initiation Visit**

Prior to study start, the monitor or PATH representative will ensure specific regulatory documents are available, such as IEC approvals, other IRB required approvals, and curriculum vitae for investigator and study staff. PATH will inform the investigator which documents need to be provided according to the applicable regulatory requirements. Prior to initiating recruitment, obtaining informed consent, and enrolling participants, the monitor or PATH representative will visit the site to train site personnel on the protocol and data collection procedures and to ensure the site meets all requirements for study start.

#### **10.1.2. Follow-up Visits**

Monitoring will be conducted according to PATH's requirements. The individuals responsible for monitoring the study will periodically review the progress of the study and should have access to all records necessary to ensure the ethical and safe conduct of the study and the integrity/validity of the recorded data.

During site visits and contacts, the monitor will:

- Check and assess the progress of the study.
- Review study data collected.
- Perform source data verification.
- Review regulatory files.
- Evaluate adherence to standard operating procedures.
- Identify any issues and address their resolution.

This will be done in order to verify that:

- The data are authentic, accurate, and complete.
- The safety and rights of participants are being protected.
- The study is conducted in accordance with the approved protocol (and any subsequent amendment) and all applicable regulatory requirements.

As part of study conduct, the investigator agrees to allow the monitor or PATH representative direct access to all relevant documents and to allocate time and the time of staff to discuss findings and any relevant issues. The investigator also agrees to allow representatives of the Foundation, authorized by PATH, to occasionally accompany the monitor or PATH representative during site visits.

#### **10.1.3. Close-out Visit**

Upon completion of the study, the study monitor or PATH representative and the investigator will conduct the following activities:

- Data clarification and/or resolution.
- Accounting, reconciliation, and destruction at sites of used and unused vaccines.
- Review of site study records for completeness.

PATH and any regulatory body retain the right to temporarily suspend or prematurely discontinue this study at any time related to safety. If the study is stopped or suspended prematurely, PATH will inform the investigator as well as regulatory authorities about the decision and the reasons for termination or

suspension. If such action is taken, all efforts must be made to ensure the safety of the participants enrolled in the study. The investigator will inform the responsible IEC and provide the reason for the suspension or termination. In case of premature study or study site closure, the monitor or PATH representative will conduct all activities as indicated above.

## **10.2. Audits and Inspections**

For the purpose of compliance with applicable regulatory guidelines it may be necessary for PATH or national or foreign regulatory authorities to conduct a site audit. This may occur at any time from start to after conclusion of the study.

The investigator agrees to allow the auditor direct access to all relevant documents and to allocate her time and the time of her staff to the auditor to discuss findings and any relevant issues.

National and foreign regulatory authorities may conduct a regulatory inspection of this study. If a regulatory authority requests an inspection, the investigator must inform PATH immediately about this request. The investigator agrees to allow the inspector(s) direct access to all relevant documents and to allocate her time and the time of her staff to discuss findings and any relevant issues.

## **10.3. Archiving**

In accordance with applicable regulatory requirements, following closure of the study, the investigator/institution will maintain a copy of study documents in a secure and designated location at the study site. Essential documents shall be retained for at least five years after the completion or discontinuation of the study.

# **11. STATISTICAL CONSIDERATIONS**

## **11.1. Study Hypothesis**

The primary study hypotheses are to prove that CD-JEV does not interfere with the immune response to measles and rubella antigens contained in the MMR vaccine.

## **11.2. Definition of Analysis Sets**

All immunogenicity analyses and summaries will be performed on a per-protocol basis which will be considered as the primary approach to immunogenicity analyses. Supportive intention-to-treat immunogenicity analyses will also be conducted on all enrolled participants who received at least one dose of study vaccines and have at least one post-vaccination serology result. Safety analyses will be conducted on an intention-to-treat basis. In the event that there are participants who do not receive the vaccine(s) to which they were randomized, safety analyses will be performed on the safety analysis set as well. Analyses set definitions are provided below.

### **11.2.1. Intention-to-Treat Analysis Set**

The Intention-To-Treat (ITT) set will include all participants who received a study vaccine. Participants in the ITT data set will be analyzed in the group to which participants have been assigned (not based on

the actual vaccine received). Participants who withdraw or are terminated from the study will be included in the ITT data set until the time of withdrawal or termination. Participants in the ITT analysis set who have at least one post-vaccination serology result will be included in the supportive immunogenicity analysis.

### **11.2.2. Safety Analysis Set**

The Safety Analysis Set (SAS) will include all participants who received a study vaccine and have at least one post-vaccination safety result. Participants in the safety data set will be analyzed based on the actual vaccine received rather than the group to which they have been randomized.

### **11.2.3. Per-Protocol Analysis Set**

The Per-Protocol (PP) sets will include the participants in the ITT set who are compliant with the protocol. This data set will be used for immunogenicity analysis only.

#### **11.2.3.1. Measles Per-Protocol Analysis Set (measles-PP)**

The measles-PP analysis set will be based on participants that meet all of the following criteria:

- Fulfilled the eligibility (inclusion/exclusion) criteria set forth in Sections 5.1. and 5.2.
- Received all study vaccines as assigned.
- Provided a valid measles serology laboratory result at baseline and at 56 days post-vaccination with MMR vaccine, with specimens taken within the windows prescribed by Section 7.14.
- Did not take any prohibited concomitant medication within 28 days post-vaccination.
- Did not show seropositivity for measles at baseline.

#### **11.2.3.2. Mumps Per-Protocol Analysis set (mumps-PP)**

The mumps-PP analysis set will be based on participants that meet all of the following criteria:

- Fulfilled the eligibility (inclusion/exclusion) criteria set forth in Sections 5.1. and 5.2.
- Received all study vaccines as assigned.
- Provided a valid mumps serology laboratory result at baseline and at 56 days post-vaccination with MMR vaccine, with specimens taken within the windows prescribed by Section 7.14.
- Did not take any prohibited concomitant medication within 28 days post-vaccination.
- Did not show seropositivity for mumps at baseline.

#### **11.2.3.3. Rubella Per-Protocol Analysis Set (rubella-PP)**

The rubella-PP analysis set will be based on participants that meet all of the following criteria:

- Fulfilled the eligibility (inclusion/exclusion) criteria set forth in Sections 5.1. and 5.2.
- Received all study vaccines as assigned.
- Provided a valid rubella serology laboratory result at baseline and at 56 days post-vaccination with MMR vaccine, with specimens taken within the windows prescribed by Section 7.14.
- Did not take any prohibited concomitant medication within 28 days post-vaccination.
- Did not show seropositivity for rubella at baseline.

#### 11.2.3.4. JE Per-Protocol Analysis Set (JE-PP)

The JE-PP analysis set will be based on participants that meet all of the following criteria:

- Fulfilled the eligibility (inclusion/exclusion) criteria set forth in Sections 5.1. and 5.2.
- Received all study vaccines as assigned.
- Provided a valid JE serology laboratory result at baseline and at 28 days post-vaccination with CD-JEV vaccine, with specimens taken within the windows prescribed by Section 7.14.
- Did not take any prohibited concomitant medication within 28 days post-vaccination.
- Did not show seropositivity for JE at baseline.

### 11.3. Analysis Plan

A full and final Statistical Analysis Plan will be specified prior to the first participant first visit and finalized before locking of the database.

#### 11.3.1. Immunogenicity

##### 11.3.1.1. Primary Hypotheses

Non-inferiority of the concomitant administration of MMR and CD-JEV vaccines (Group 1) to MMR and CD-JEV vaccines given 2 months apart (Group 2) in children 9 months of age at 56 days is established in terms of percentage (or proportions) of participants achieving seropositivity to measles and rubella assuming a non-inferiority margin of 10%.

The following co-primary hypotheses will be tested:

$$H_{0M}: (P_{(M1)} \text{ minus } P_{(M2)}) \leq -10\%$$

$$H_{1M}: (P_{(M1)} \text{ minus } P_{(M2)}) > -10\%$$

and

$$H_{0R}: (P_{(R1)} \text{ minus } P_{(R2)}) \leq -10\%$$

$$H_{1R}: (P_{(R1)} \text{ minus } P_{(R2)}) > -10\%$$

where  $P_{(M1)}$  refers to the percentage of participants seroconverting to measles in Group 1 and  $P_{(M2)}$  refers to the percentage of participants seroconverting to measles in Group 2 and where  $P_{(R1)}$  refers to the percentage of participants seroconverting to rubella in Group 1 and  $P_{(R2)}$  refers to the percentage of participants seroconverting to rubella in Group 2.

#### 11.3.2. Safety

To evaluate safety, proportions of participants experiencing any category of adverse event will be calculated with corresponding 95% confidence intervals using the Exact test.

#### 11.3.3. Analysis and Reporting of Withdrawals

Participants may withdraw from the study at any time and for any reason. The investigator may withdraw participants from the study for various reasons. These reasons and how to handle withdrawals are detailed in Section 5.3. Regardless of reason for withdrawal, it is the obligation of the investigator and sponsor to report these withdrawals as part of the analyses, the clinical study report, and peer-reviewed

publication(s) summarizing study results. Withdrawals will be summarized with their reasons in these reports.

## 11.4. Sample Size Considerations

An enrollment size of 628 participants (314 per treatment group) was targeted to achieve an overall power of 90% (approximate individual power of 95% for each co-primary objective). This estimation is based upon a non-inferiority margin of 10% and a one-sided type-one error rate of 2.5% or less, and assumes (based on historical data) a 95% seropositivity rate for measles vaccine, a 90% seropositivity rate for rubella vaccine, and approximately 20% non-evaluable rate (exclusion for baseline seropositivity and loss to follow-up) at 56 days post-vaccination. Individual sample size calculations were based on Farrington-Manning score test.

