#### Sample Size and Power Estimation

Enrollment size of 628 participants (314 per treatment group) was targeted to achieve an overall power of 90% (approximate individual power of 95% for each co-primary objective). This estimation is based upon a non-inferiority margin of 10%, a one-sided significance level of 2.5%, and assumed (based on historical data) a 95% seropositivity rate for measles vaccine, a 90% seropositivity rate for rubella vaccine, and a 20% non-evaluable rate at 56 days post-vaccination. Individual sample size calculations were based on the Farrington-Manning score test.

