## **2. BACKGROUND INFORMATION AND SCIENTIFIC RATIONALE**

### **2.1. Background Information**

#### **2.1.1. Measles Virus and Vaccination**

Measles virus is an enveloped, single-stranded RNA virus affecting only humans. The virus causes high fever, cough, maculopapular rash, coryza, and conjunctivitis. Complications from the disease include otitis media, laryngo-tracheobronchitis, diarrhea, pneumonia, and in very severe cases, death. Measles is highly infectious through aerosolized respiratory droplets and by direct contact; in the prevaccine period, >90% of individuals were infected by 10 years of age. Before the introduction of measles vaccines, measles virus caused an estimated five to eight million deaths per year. Wide scale introduction of safe and effective measles vaccines has greatly reduced the burden of this disease—from 2000 through 2011, the number of deaths from measles dropped from an estimated 548,000 to 158,000 per year worldwide.

The recommended age for measles immunization in developing countries with ongoing transmission in which the risk of measles mortality among infants remains high is 9 months of age. In countries with low rates of measles transmission, the vaccine is recommended at 12 months of age to take advantage of the higher seroconversion rates achieved at this age. The proportion of children who develop protective antibody levels following measles immunization depends on the presence of inhibitory maternal antibodies and the immunologic maturity of the vaccine recipient. Approximately 85% of children develop protective antibody levels after one dose of measles at 9 months of age; this rate is much lower in children <9 months of age. Thus, routine immunization for measles is not given in children below 9 months.

Since population immunity needs to be >90% in all districts to prevent measles epidemics, high immunization coverage is the cornerstone of effective measles control and the World Health Organization (WHO) now recommends two doses of measles vaccine for all children to ensure adequate immunity. WHO also recommends that countries take the opportunity offered by accelerated measles control and elimination activities to introduce rubella-containing vaccines.

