#### **2.1.3. Rubella Virus and Vaccination**

Rubella is an enveloped single-stranded RNA virus. Transmitted by the respiratory route, humans are the sole host of the virus. Rubella disease is a mild, self-limited illness that usually occurs during childhood. It may include a prodromal illness consisting of fever <39.0°C, malaise, and mild conjunctivitis followed by postauricular, occipital, and posterior cervical lymphadenopathy and a maculopapular, erythematous and often pruritic rash. Post infectious encephalitis occurs in approximately 1/6000 rubella cases. Rubella

infection occurring just before conception and during early pregnancy may result in miscarriage, fetal death, or congenital defects (including congenital heart disease, cataracts, neurosensory deafness, mental retardation and intrauterine growth retardation) known as congenital rubella syndrome (CRS). Rubella usually occurs in a seasonal pattern, with epidemics every 5-9 years. In countries that have not introduced rubella vaccine, the burden of CRS may be high; in 1996 an estimated 46,000 children were born with CRS in South-East Asia. High rubella vaccine coverage has significantly reduced or eliminated rubella and CRS in both developed and developing countries.

Since rubella is not as highly infectious as measles and because the effectiveness of one dose of a rubella containing vaccine is  $\geq 95\%$  when given at 9 months of age, only one dose of rubella vaccine is required to achieve rubella elimination if high coverage is achieved. However, the WHO Strategic Advisory Group of Experts (SAGE) Working Group on Measles and Rubella recently clarified its position through the following recommendation: 1) rubella-containing vaccine should be given in combination with measles-containing vaccine (MCV) as measles-rubella (MR) or MMR and 2) in countries using rubella-containing vaccine in combination with MR or MMR, the same formulation should be used for both doses (either MR or MMR).

[figure not shown]

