**Table 2. Seropositivity rates and anti-measles IgG geometric mean concentrations and anti-JE geometric mean titers in Philippine infants vaccinated with JE and measles vaccines.**

		Group 1 (CD-JEV then MV) (N=88)		Group 2 (concomitant) (N=219)		Group 3 (MV then CD-JEV) (N=178)	
		% seropositive (95% CI)	GMC/GMT (95% CI)	% seropositive (95% CI)	GMC/GMT (95% CI)	% seropositive (95% CI)	GMC/GMT (95% CI)
Measles vaccine response (anti-measles IgG)	Day 0	1.1 (0.0-6.2)	12.8 a (10.2-16.2)	0.0 (0.0-1.7)	7.4 (6.3-8.8)	0.0 (0.0-2.1)	7.0 (5.8-8.5)
	Day 28	88.6 (80.1-94.4)	318.9 (273.0-372.6)	91.8 (87.3-95.1)	301.9 (269.0-338.9)	86.5 (80.6-91.2)	262.5 (222.2-310.2)
JE vaccine response (anti-JE neutralizing antibody)	Day 0	3.4 (0.7-9.6)	5.7 (4.9-6.5)	5.4 (2.8-9.3)	5.7 (5.2-6.1)	6.1 (3.1-10.7)	5.9 (5.3-6.6)
	Day 28	92.1 (84.3-96.7)	202.8 (140.5-292.9)	90.5 (85.9-94.1)	155.0 (123.5-194.5)	90.6 (85.3-94.4)	139.4 (109.5-177.5)
	Year 1	90.2 (82.2-95.4)	106.8 (71.5-159.4)	84.0 (78.3-88.6)	80.7 (62.4-104.3)	85.9 (80.5-90.3)	74.9 (59.2-94.9)
	Year 2	81.7 (72.4-89.0)	68.8 (47.3-100.1)	83.0 (77.3-87.8)	61.6 (49.1-77.4)	81.7 (75.8-86.6)	70.1 (54.6-90.1)
	Year 3	79.6 (70.0-87.2)	49.9 (36.5-68.3)	81.9 (75.9-86.8)	45.7 (37.2-56.3)	82.6 (76.8-87.4)	59.3 (47.1-74.8)

CD-JEV: live, attenuated Japanese encephalitis SA 14-14-2 vaccine; MV: measles vaccine; N: number of infants in the per protocol analysis; CI: confidence interval; GMC: milli International Units per milliliter (mIU/mL), seroprotection defined as  $\geq 120$  mIU/mL; GMT: geometric mean titer, seroprotection defined as  $\geq 1:10$ .

a Although measles GMC/GMT at baseline were higher in Group 1, the GMC/GMT 28 days after vaccination were not significantly different.

Seroresponse rates to CD-JEV may not be equal in all pediatric populations. A lot-to-lot consistency study conducted in 2012 among 10-month-old Bangladeshi infants in a rural area with a low incidence of JE demonstrated a seropositivity rate of only 82.3% (95% CI 79.0-85.2%) following a single vaccine dose. The reasons for this lower response rate are unclear, but may be related to the high rates of malnutrition found in the population or other population-specific causes. Nevertheless, these findings highlight the value of assessing the performance of the vaccine in other high-risk populations.

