#### 2.3. Sample Size and Power

An enrollment size of 628 participants (314 per treatment group) was targeted to achieve an overall power of 90% (approximate individual power of 95% for each coprimary objective). This estimation is based upon a non-inferiority margin of 10% and a one-sided type-one error rate of 2.5% or less, and assumes (based on historical data) a 95% seropositivity rate for measles vaccine, a 90% seropositivity rate for rubella vaccine, and approximately 20% non-evaluable rate (exclusion for baseline seropositivity and loss to follow-up) at 56 days post-vaccination. The sample size calculations were based on the Farrington-Manning score test.

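### Is the stated power of 90% wrong, or undermined by an unexplained 95% measles rate?

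*Protocol*

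**What the plan says.** Protocol 11.4 sets enrolment at 628 (314 per group), "targeted to achieve an overall power of 90% (approximate individual power of 95% for each co-primary objective"). The inputs are a 10-point margin, a one-sided error of 2.5%, 1:1 allocation, about 20% non-evaluable, and the Farrington-Manning score test applied to each endpoint separately. On response rates the section "assumes (based on historical data) a 95% seropositivity rate for measles vaccine, a 90% seropositivity rate for rubella vaccine". The Protocol Summary ("assumed (based on historical data) a 95% seropositivity rate for measles vaccine") and SAP 2.3 ("targeted to achieve an overall power of 90% (approximate individual power of 95% for each coprimary objective") repeat this. Protocol 2.2 puts the power differently, as a minimum of 90 per cent that depends on the assumed response and retention. Success requires both antigens to pass (Protocol 11.5.1, SAP 6.2).

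The background sections carry other response figures. Protocol 2.1.1: "Approximately 85% of children develop protective antibody levels after one dose of measles at 9 months of age". Table 2 in Protocol 2.1.6, from an earlier Philippine trial, gives Day 28 measles seropositivity of "91.8 (87.3-95.1") with concomitant vaccination, "86.5 (80.6-91.2") with measles vaccine first, and 88.6% with CD-JEV first. For rubella, Protocol 2.1.3 says that "the effectiveness of one dose of a rubella containing vaccine is" 95% or more at 9 months.

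**The concern.** Two things look wrong.

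First, with the plan's own inputs the calculated power is not 95% for each endpoint and 90% overall. Measles comes out far higher and the overall figure about five points higher. When stated power cannot be recovered from stated inputs, there may be an error in the sample size, or an input that the text does not give.

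Second, the measles rate of 95% is above all four one-dose point estimates in the protocol's background, and its only support is a reference to historical data. In a non-inferiority comparison of high proportions, power falls as the common rate moves down from 95%, because the variance grows. If the true rate were in the mid-80s, the chance of passing both endpoints would drop below the 90% target. A co-administration schedule that causes no interference could then fail through imprecision.

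**Working it through.** **Inputs.** From Protocol 11.4: margin 0.10, one-sided alpha 0.025 (z = 1.960), individual power 0.95 (z = 1.645), rates 0.95 and 0.90, 20% non-evaluable. One assumption is added: the same true rate in both groups. It is the natural reading of one rate per antigen, though the text does not spell it out.

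**Method.** Farrington-Manning: n per group = [(1.960 × s0 + 1.645 × s1) / 0.10]². Here s1 = √(2p(1 − p)), and s0 uses the two rates fitted under a difference of exactly −10 points.

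*Rubella, p = 0.90.* Fitted rates 0.8313 and 0.9313; s0 = √(0.8313 × 0.1687 + 0.9313 × 0.0687) = 0.4519; s1 = 0.4243. n = [(0.8856 + 0.6979) / 0.10]² = 250.7, so 251. Enrolled: 251 / 0.80 = 313.75, so 314 per group and **628 in total. This is the plan's figure.**

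*Measles, p = 0.95.* Fitted rates 0.8703 and 0.9703; s0 = 0.3764; s1 = 0.3082. n = [(0.7377 + 0.5070) / 0.10]² = 154.9, so 155, or 194 enrolled per group.

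Rubella therefore sets the sample size.

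**Power at 251 evaluable per group.** Power = Φ[(0.10 × √251 − 1.960 × s0) / s1], with 0.10 × √251 = 1.5843.

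- Measles: (1.5843 − 0.7377) / 0.3082 = 2.747, power 99.7%.
- Rubella: (1.5843 − 0.8856) / 0.4243 = 1.647, power 95.0%.
- Both, if independent: 0.9970 × 0.9502 = 94.7%. Under any dependence it lies between 0.9970 + 0.9502 − 1 = 94.7% and 95.0%.

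Exact enumeration gives 99.8% and 95.5%, so the approximation is not the issue.

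**Where the stated 95% and 90% come from.** Size each endpoint at 95% and combine: 0.95 × 0.95 = 90.25%, or 0.95 + 0.95 − 1 = 90% as the lower bound under any dependence. Taking the larger of the two sample sizes gives measles more than its 95%. Under the stated inputs, 211 evaluable per group would already give 90.0% overall. Non-evaluable participants could therefore reach 1 − 211/314 = 32.8% before the target was missed.

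**If the measles rate is lower** (251 evaluable, independence, equal rates):

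| Measles rate | Source in protocol | Measles power | Overall, rubella 90% (× 0.9502) | Overall, rubella 95% (× 0.9970) |
|---|---|---|---|---|
| 95% | 11.4 | 99.7% | 94.7% | 99.4% |
| 91.8% | Table 2 | 97.3% | 92.5% | 97.0% |
| 88.6% | Table 2 | 92.9% | 88.3% | 92.6% |
| 86.5% | Table 2 | 89.5% | 85.1% | 89.3% |
| 85% | 2.1.1 | 87.1% | about 83% | 86.8% |

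With rubella at 90%, overall power reaches 90% at a measles rate of 89.8%. The rubella 95% column borrows the figure in 2.1.3, which is effectiveness rather than seropositivity, so it is only illustrative.

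**If fewer infants are non-evaluable.** The 20% covers baseline seropositivity as well as loss to follow-up. Table 2 shows baseline measles seropositivity of only 0.0% to 1.1% (by IgG). Taking 10% as an assumption gives 314 × 0.90 = 282.6, so 283 per group. Then:

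- With rubella at 90%, the measles rate needed for 90% overall falls to 86.5%.
- A measles rate of 88.6% gives 92.5% overall.
- A measles rate of 85% gives 88.0% with rubella at 90%, and 90.6% with rubella at 95%.

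**Are the measles figures like for like?** The primary endpoint is neutralising antibody by PRNT, 56 days after MMR, in infants seronegative at baseline (Protocol 3.2.1 and 11.2.3.1). Table 2 is IgG, 28 days after measles vaccine. It uses the same numerical cut-off of 120 mIU/mL, but on a different assay, day and vaccine. Section 2.1.1 is general background with no assay given. One Table 2 interval also reaches 95.1%.

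**The case for a change.** The strongest case for a change leaves the stated targets aside and rests on the measles rate. Three of the four background point estimates (85%, 86.5% and 88.6%) put overall power below 90% at the planned 20% non-evaluable and rubella at 90%. At 85% no dependence between the endpoints rescues it: the bounds are 82.1% to 87.1%. If assay and timing justify 95%, one sentence would say so, and none does. Equal true rates are also assumed without saying so, although Protocol 2.2 cites interference between yellow fever vaccine and MMR as a reason for the trial. A true deficit of one point on each antigen, an assumed figure, would give 0.9828 × 0.8899 = 87.5% overall.

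The arithmetic stands. The text does not name rubella as the driver or give the source of the 95%, and a reader would be better served if it did. But these results fix the other inputs at their planned values. Retention and baseline seropositivity could move power the other way, and Protocol 2.2 already makes its power statement conditional on both kinds of assumption. Sizing a non-inferiority trial at zero true difference is conventional, and the one-point deficit has no source in the documents. Even on its own terms this argument asks only for explanatory text and leaves enrolment at 628.

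**Conclusion.** The concern does not hold as an error. The sample size reproduces to the participant, and the stated powers are minimum targets that the design meets: 99.7% for measles, 95.0% for rubella and about 95% overall, against targets of about 95% each and 90% overall. The difference is in the safe direction.

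The 95% measles rate is unexplained but not contradicted, because the lower figures are not measurements of this endpoint. The exposure is bounded: at 20% non-evaluable and rubella 90%, overall power runs from about 83% (measles 85%) to 92.5% (measles 91.8%), and it is higher with better retention or a higher rubella rate. All of this assumes equal true rates in the two groups, and the overall figures also assume independence, which hardly matters at the planned inputs.

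The missing detail has no bearing on how the trial is run or read. The non-inferiority conclusion rests on the confidence interval against −10 points, whatever power was planned. Low power would raise the chance of failing to show non-inferiority; it would not raise the chance of a false claim. No change to the plan follows.
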